We plan to evaluate participant satisfaction on a 10 point Likert scale immediately after the procedure in participants randomized to activated TENS units and placebo TENS units.

3 Study Design

3.1 *General Description*

The study is a two arm phase III double blinded randomized placebo control trial looking at the effect of TENS unit on pain in participants receiving Office based Cystoscopic Onabotulinum Toxin A injection for Overactive bladder at the Mayo Clinic in Rochester, Minnesota.

3.2 Number of Subjects: 60 subjects**3.3 Duration of Participation:** From accrual to the end of the Cystoscopic Onabotulinum Toxin A injection office visit**3.4 Study Schema and Flow:**

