Following the initiation/placement of the TENS unit, the study coordinator and fellowship trained Urogynecologist will enter the room. Rigid cystoscopic Intradetrusor Onabotulinumtoxin A injection will be performed by a fellowship trained Urogynecologist. This involves 100 units of Onabotulinumtoxin A injected in roughly 20 aliquots throughout the bladder. After the procedure participants are discharged home.

Care providers performing the injection will only be allowed into the procedure room once the TENS units has been activated. The nursing staff will assess the pad placement sites for any skin irritation, and or burns. If so, this will be documented on the participant’s electronic medical record. The study coordinator will ask the participant and the provider separately (in the absence of the other) whether they felt the participant was in the Active TENS group versus the Sham TENS group at the end of the procedure. Participants will be advised to call and inform the clinic if they experience any burns, skin irritation or muscle soreness/pain.

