5.3 Masking/Blinding

Participants in both arms of the study will be blinded to whether they received Active TENS unit or Sham TENS unit. Only the nursing team will be notified about the randomization. The care providers performing the procedure and the study coordinator will not be notified about the randomization. The study coordinator will ask the participant and the provider separately (in the absence of the other) whether they felt the participant was in the Active TENS group versus the Sham TENS group at the end of the procedure.

Schedule of Events		
Study Activity	Visit 1 Outpatient Clinic	Visit 2 Outpatient Procedure Cystoscopic Onabotulinum Toxin A Injection
Screening and Informed Consent	X	
Depression and Anxiety Screen		X
Randomization		X
Numerical Pain Score assessment		X
Participant Satisfaction Assessment		X
Participant and Provider Perception regarding Arm of study		X

6 Statistical Plan

6.1 *Sample Size Determination:*

Based on our baseline preliminary data and the study ‘Transcutaneous Nerve Stimulation for Pain Relief During Office Hysteroscopy’ by Lison et al (2017)[6], power calculations were performed. As estimates of the mean and variance of the pain scale we used table 2 from the Lison et al (2017) study and our preliminary data. Group sample sizes of 27 and 27 achieve 80.53% power to reject the null hypothesis of equal means when the population mean difference is $\mu_1 - \mu_2 = 4.0 - 2.0 = 2.0$ with standard deviations of 2.0 for group 1 and 3 for group 2, and with a significance level (alpha) of 0.050 using a two-sided two-sample unequal-variance t-test. With a 10% possible dropout rate, we plan to have 30 participants in each of the study.

6.2 *Statistical Methods:*

6.2.1 **Specific Aim #1: To assess whether the TENS units is effective for intraoperative pain management during office cystoscopic Intradetrusor Onabotulinumtoxin A in women with OAB.**

We plan to compare participant reported pain using a 0-10 numerical pain scale at baseline, during and after cystoscopic intradetrusor onabotulinumtoxin A injection in participants randomized to active TENS units and placebo TENS units. We will compare the change in numerical pain scale from baseline to intraoperatively and intraoperatively to postoperatively between both groups.

Hypothesis: We hypothesize that there will be a clinically significant pain reduction in the Active TENS group.

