And/or per protocol may be problems/events that in the opinion of the sponsor-investigator may have adversely affected the rights, safety, or welfare of the subjects or others, or substantially compromised the research data.

Other important medical events are those that may not be immediately life threatening, but are clearly of major clinical significance include:

- Burns
- Skin Irritation
- Muscle Pain or Soreness

All adverse events that do not meet any of the criteria for serious, should be regarded as **non-serious adverse events**.

Adverse Event Reporting Period

For this study, the study treatment follow-up period is defined as from enrollment to 1 week after receiving the cystoscopic Onabotulinum Toxin A injection.

Preexisting Condition

A preexisting condition is one that is present at the start of the study. A preexisting condition should be recorded as an adverse event if the frequency, intensity, or the character of the condition worsens during the study period.

General Physical Examination Findings

At screening, any clinically significant abnormality should be recorded as a preexisting condition. At the end of the study, any new clinically significant findings/abnormalities that meet the definition of an adverse event must also be recorded and documented as an adverse event.

Post-study Adverse Event

All unresolved adverse events should be followed by the sponsor-investigator until the events are resolved, the subject is lost to follow-up, or the adverse event is otherwise explained. At the last scheduled visit, the sponsor-investigator should instruct each subject to report, to the sponsor-investigator, any subsequent event(s) that the subject, or the subject's personal physician, believes might reasonably be related to participation in this study.

Abnormal Laboratory Values

No abnormal laboratory values are related to the administration of the TENS Unit

Hospitalization, Prolonged Hospitalization or Surgery

Any adverse event that results in hospitalization or prolonged hospitalization should be documented and reported as a serious adverse event unless specifically instructed otherwise in this protocol. Any condition responsible for surgery should be documented as an adverse event if the condition meets the criteria for an adverse event.

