7.2 Recording of Adverse Events

At each contact with the subject, the study team must seek information on adverse events by specific questioning and, as appropriate, by examination. Information on all adverse events should be recorded immediately in the source document, and also in the appropriate adverse event section of the case report form (CRF). All clearly related signs, symptoms, and abnormal diagnostic, laboratory or procedure results should be recorded in the source document.

All adverse events occurring during the study period must be recorded. The clinical course of each event should be followed until resolution, stabilization, or until it has been ultimately determined that the study treatment or participation is not the probable cause. Serious adverse

events that are still ongoing at the end of the study period must be followed up, to determine the final outcome. Any serious adverse event that occurs during the Adverse Event Reporting Period and is considered to be at least possibly related to the study treatment or study participation should be recorded and reported immediately.

CTCAE Version 5.0 (November 27, 2017) will be used for classification and grading of Adverse Events:

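### Adverse events are to be followed for 1 week after injection, but no contact is scheduled after the procedure visit, so later skin and muscle events are likely under-ascertained

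*Combined protocol and SAP*

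**What the plan says.** All references are to the combined protocol and SAP.

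- **Length of follow-up.** Section 7.1 (Adverse Event Reporting Period) defines it as "from enrollment to 1 week after receiving the cystoscopic Onabotulinum Toxin A injection".
- **Length of participation.** Section 3.3 gives "From accrual to the end of the Cystoscopic Onabotulinum Toxin A injection office visit". The Study Summary gives 2 days.
- **Scheduled contacts.** The last column of the Schedule of Events is "Visit 2 Outpatient Procedure Cystoscopic Onabotulinum Toxin A Injection". No call or visit follows it, and no row is given to adverse events.
- **At the procedure visit (Section 5.2).** "The nursing staff will assess the pad placement sites for any skin irritation, and or burns". Then, "After the procedure participants are discharged home".
- **After discharge.** Section 5.2: "Participants will be advised to call and inform the clinic if they experience any burns, skin irritation or muscle soreness/pain". Section 7.1 (Post-study Adverse Event) adds that, at the last visit, participants are told to report later events that might be related to the study.
- **Questioning.** Section 7.2 (Recording of Adverse Events): "At each contact with the subject, the study team must seek information on adverse events by specific questioning".
- **Use of the data.** The Stopping Rules section halts recruitment and use of the TENS unit if more than 3 serious events are reported in the first 30 participants. Its examples are severe skin reactions, burns and muscle weakness.

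**The concern.** The period for which events are to be recorded is a week longer than the period in which anyone is scheduled to ask about them. The duty in Section 7.2 to question participants applies only when there is a contact, and none is planned after discharge.

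The events in question are the ones the protocol itself singles out. Section 7.1 lists burns, skin irritation and muscle pain or soreness as important medical events. Section 5.2 asks participants to call about the same three, so the plan allows that they may appear after the visit. The pad-site check can find skin effects present that day. It cannot find muscle soreness or anything that develops later.

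At stake is the completeness of the safety record. Section 7.2 requires every event in the study period to be recorded, and with passive reporting after discharge this cannot be shown. The 24-hour notification of serious events in Section 7.3.1 likewise depends, after discharge, on how soon the participant calls. Any under-reporting of serious events would also make the stopping rule less sensitive.

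**Working it through.** **Step 1. The plan's own figures.** The plan gives no event rate, capture rate or operating characteristic for safety, so there is nothing on this point to reproduce. The stated power of 80.53% with 27 per group does reproduce (Welch t-test, Satterthwaite df 45.3), but it does not bear on this question and does not change if a safety contact is added.

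**Step 2. Ascertainment over the stated week.**

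| Time | What the plan provides | Kind of capture |
|---|---|---|
| Procedure visit | Pad-site check by nursing staff (5.2, skin only); questioning at a contact (7.2) | Active |
| Before leaving, and at 24 hours | Case report forms checked for completeness (8.3.4, 8.3.3) | Check of forms; the 24-hour step is not a participant contact |
| Discharge to 1 week | Advice to call (5.2); instruction to report later events (7.1) | Participant-initiated |
| End of the 1-week period | Nothing scheduled | None |

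Active capture therefore ends at the visit. Nothing is scheduled at the end of the week that would separate a participant who had no event from one who had an event and did not call.

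**Step 3. Illustration for the stopping rule.** The inputs are:

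- n = 30, and a threshold of more than 3, that is at least 4 (Stopping Rules).
- p, the true share of participants with an event that counts towards the rule, at most one per participant. **Assumption**, varied over 5%, 10% and 15%.
- a, the share of those events that reach the record. **Assumption**, varied over 100%, 75% and 50%.

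With q = p × a, the chance of reaching the rule is

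P(X ≥ 4) = 1 − Σ (k = 0 to 3) C(30, k) q^k (1 − q)^(30 − k).

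For p = 10% and a = 50%, q = 0.05. The four terms are 0.2146, 0.3389, 0.2586 and 0.1270, which sum to 0.939, so P = 0.061.

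| True rate p | a = 100% | a = 75% | a = 50% |
|---|---|---|---|
| 5% | 0.061 | 0.025 | 0.006 |
| 10% | 0.353 | 0.184 | 0.061 |
| 15% | 0.678 | 0.441 | 0.184 |

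Incomplete capture lowers the chance of reaching the rule in every row. The absolute loss depends heavily on the assumed rate. From full to 75% capture it is 0.061 − 0.025 = 0.036 at a 5% rate, and 0.678 − 0.441 = 0.237 at 15%.

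**The case against.** **Participant-initiated reporting is a stated method.** Participants are expressly told to call about these three events and are told again at the last visit to report later ones. If they call, the questioning duty applies to that contact, and unresolved events must be followed. A reporting window served by participants' calls is not in itself contradictory, and for a brief, non-invasive intervention it may be thought sufficient. This stands in part: post-discharge reporting is invited, not merely unsolicited. It remains passive, and Section 3.3 and the Study Summary still end participation before the window closes.

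**The stopping rule may hardly be touched.** A reader might infer that the rule would work on a serious undercount. The documents do not support that. The rule counts serious events, and of its examples only burns clearly match the three events participants are asked to call about. The status of irritation and soreness is unclear, since Section 7.1 lists them as other important medical events. Severe skin reactions and burns are also those likeliest to be seen at the pad-site check or to prompt a call. If the true rate is low, capture makes little difference: at 5% the rule is reached with probability 6.1% or 2.5%. This objection stands.

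**No 1-week safety claim is planned.** A reader might also infer that the trial intends to conclude that TENS is safe to 1 week. No safety endpoint, 1-week event rate or conclusion of that kind appears in the objectives, endpoints or statistical plan. This stands too. The issue is the meaning of whatever adverse event counts are reported.

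**The evidence of absence is incomplete.** The Section 3.4 flow chart was not in the text I worked from and could show a later contact. The Schedule of Events also omits the procedure-day skin check, so it is not a full list of safety activities. These are fair cautions, but three separate places end at the procedure visit and none points to a later contact.

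**Conclusion.** The point holds as a gap in safety ascertainment. Follow-up is defined to 1 week, participation and scheduled contact end at the procedure visit, and events that appear after discharge are recorded only if the participant calls. Events over the stated week are therefore likely under-ascertained. By how much cannot be derived from the documents.

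The effect on the stopping rule is uncertain. The probabilities shown rest on assumed event and capture rates and on at most one counted event per participant. They show the direction and how strongly the result depends on the assumed rate; they do not predict what will happen in this trial. The conclusion also assumes that the Section 3.4 flow chart shows no later contact.

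The pain and satisfaction analyses are unaffected, because those scores are all collected at the procedure visit.

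**What to change.** Reconcile Section 3.3, the Study Summary and the Schedule of Events with Section 7 by adding one adverse event contact at 1 week. The existing study coordinator, who is blinded to allocation, can make it as a brief call or portal message, with the same fixed questions in both arms on burns, skin irritation and muscle pain or soreness, plus an open question on anything else. Record the answer even when it is no event, and record when the contact could not be made.

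The cost is about 60 short contacts (2 arms × 30 participants). No extra visit, procedure or participants are needed, and the sample size is unchanged. The contact falls after every pain and satisfaction score has been collected, so it cannot influence them.

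If no contact is added, the report should present events after the visit as participant-initiated reports only, separately from those found at the visit, and should not express them as a 1-week rate.

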7.2 Recording of Adverse Events

At each contact with the subject, the study team must seek information on adverse events by specific questioning and, as appropriate, by examination. Information on all adverse events should be recorded immediately in the source document, and also in the appropriate adverse event section of the case report form (CRF). All clearly related signs, symptoms, and abnormal diagnostic, laboratory or procedure results should be recorded in the source document.

All adverse events occurring during the study period must be recorded. The clinical course of each event should be followed until resolution, stabilization, or until it has been ultimately determined that the study treatment or participation is not the probable cause. Serious adverse

events that are still ongoing at the end of the study period must be followed up, to determine the final outcome. Any serious adverse event that occurs during the Adverse Event Reporting Period and is considered to be at least possibly related to the study treatment or study participation should be recorded and reported immediately.

CTCAE Version 5.0 (November 27, 2017) will be used for classification and grading of Adverse Events:

7.3 Reporting of Serious Adverse Events and Unanticipated Problems

When an adverse event has been identified, the study team will take appropriate action necessary to protect the study participant and then complete the Study Adverse Event section of the Case Report Form. The sponsor-investigator will evaluate the event and determine the necessary follow-up and reporting required.

7.3.1 Investigator reporting: notifying the Mayo IRB

The study coordinator will promptly report to the Principal Investigator and co- investigators of “any unanticipated problems involving risk to subjects or others” (UPIRTSO) as defined by the Code of Federal Regulations [45 CFR 46.103(b)(5) and 21 CFR 56.108(b)(1)]. The adverse events will be documented on the CRF and the data management system.

The investigator will review all adverse event reports to determine if specific reports need to be made to the IRB. The investigator will sign and date the adverse event report when it is reviewed. For this protocol, only directly related SAEs/UPIRTSOs will be reported to the IRB.

Investigators will collect, assess, and report all adverse events that occur during a clinical trial. The investigators will review each event and ensure the appropriate information is added to the case report form (CRF). If the event is serious, the internal reviewer (as appointment by the Mayo Clinic Obstetrics and Gynecology Department Research chair) and the Mayo Clinic IRB must be informed within 24 hours of the occurrence of the event. Non-serious events will also be reported to the internal reviewer and the Mayo Clinic IRB sponsor through documentation on the CRF and database updates. Any adverse event will be reported to the Mayo IRB, in the manner prescribed by Mayo’s policy. [IRB Policy Document No. 10049, Procedure for the Investigator]. Once reported, the Mayo Clinic IRB will determine what constitutes an unanticipated problem involving risk to subjects or others (UPIRTSO) and will report to appropriate institutional officials, OHRP, and other relevant Federal agencies as set forth in IRB Policy III.C.

Information collected on the adverse event worksheet (*and entered in the research database*):

- Subject name:
- Medical record number:
- Disease/histology (if applicable):
- The date the adverse event occurred:
- Description of the adverse event:
- Relationship of the adverse event to the research (drug, procedure, or intervention*):
- If the adverse event was expected:
- The severity of the adverse event: (use a table to define severity scale 1-5**)
- If any intervention was necessary:
- Resolution: (was the incident resolved spontaneously, or after discontinuing treatment)
- Date of Resolution:

The relationship of an AE to the Investigational Drug is a clinical decision by the sponsor-investigator (PI) based on all available information at the time of the completion of the CRF and is graded as follows:

1. Not related: a reaction for which sufficient information exists to indicate that the etiology is unrelated to the study drug; the subject did not receive the study medication or the temporal sequence of the AE onset relative to administration of the study medication is not reasonable or the event is clearly related to other factors such as the subject's clinical state, therapeutic intervention or concomitant therapy.
2. Unlikely: a clinical event, including laboratory test abnormality, with a temporal relationship to drug administration which makes a causal relationship improbable and in which other drugs, chemicals, or underlying disease provide plausible explanations.
3. Possible: a clinical event, including laboratory test abnormality, with a reasonable time sequence to administration of the drug but which could also be explained by concurrent disease or other drugs or chemicals; information on drug withdrawals may be lacking are unclear.
4. Probable: a clinical event including laboratory test abnormality, with a reasonable time sequence to administration of the drug, unlikely to be attributed to concurrent disease or other drugs or chemicals and which follows a clinically reasonable response on withdrawal (de-challenge): re-challenge information is not required to fulfill this definition.
5. Definite: a reaction that follows a reasonable temporal sequence from administration of the drug, or in which the drug level has been established in body fluids or tissues, that follows a known or expected response pattern to the suspected drug, and that is confirmed by improvement on stopping or reducing the dosage of the drug, and reappearance of the reaction on repeated exposure (re-challenge).

The maximum intensity of an AE during a day should be graded according to the definitions below and recorded in details as indicated on the CRF. If the intensity of an AE changes over a number of days, then separate entries should be made having distinct onset dates.

1. Mild: AEs are usually transient, requiring no special treatment, and do not interfere with patient's daily activities.
2. Moderate: AEs typically introduce a low level of inconvenience or concern to the patient and may interfere with daily activities, but are usually ameliorated by simple therapeutic measures.
3. Severe: AEs interrupt a patient's usual daily activity and traditionally require systemic drug therapy or other treatment.

7.1 Stopping Rules

An interim analysis will be performed after 30 participants have undergone cystoscopic Onabotulinum Toxin A injection as part of the study. The information will also be sent to an internal reviewer (as appointment by the Mayo Clinic Obstetrics and Gynecology Department Research chair). At this point a meeting between the investigators and internal reviewer will be convened to discuss the existing data, the efficacy and any safety issues including serious adverse events that have taken place. A decision will be made as to whether to continue with the study or to prematurely terminate the study based on any safety issues.

If there are greater than 3 serious adverse (i.e. severe skin reactions, burns, muscle weakness) events reported in the 30 participants reviewed, further recruitment and administration of the TENS unit will be stopped. The study will be put on hold with the IRB and each of the adverse events will be carefully looked into for any causal relation to the TENS unit. If no causal relationship is proved then the will re-approach IRB for restarting the study.

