4.3 Subject Recruitment, Enrollment

All women with a diagnosis of Overactive bladder who are pursuing Office Cystoscopic Onabotulinum Toxin A for treatment and receiving care at the Division of Urogynecology, Mayo Clinic in Rochester, Minnesota will be approached for this study. Fellows, residents, Advanced level providers and Urogynecologists can offer these participants to talk with the study coordinator. The study coordinator will then be notified of women with Overactive Bladder interested in office based Cystoscopic Intra-detrusor Onabotulinum Toxin A injections by the care provider/Registered Nurse during the office visits following their appointment. The study coordinator will then approach the women interested in the study immediately following this appointment. The study coordinator will make sure that the participant meets the inclusion and exclusion criteria for the study. A written informed consent will be obtained from all eligible women who chose to participate using a standardized consent form approved by the Mayo Clinic Institutional Review Board. We will allow for 1 year from the start of recruitment for accrual of participants, expecting to enroll approximately 5 participants per month. A total of 60 participants will be recruited with 30 participants in each group (Active TENS group and Sham TENS group).

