Participants will be randomized to two groups using a computerized sequence generator based on permuted block randomization (1:1 allocation ratio) on the day of the procedure by the registered nurse (RN) taking care of the participant. Participants in Group 1 will receive an Activated TENS unit for pain control. Participants in Group 2 will have a Sham, inactive TENS unit for pain control. Both groups will be blinded to the type of TENS unit received. The nursing team taking care of the participant will know about the randomization. The care providers performing the procedure and the study coordinator will not be notified about the randomization.

On the day of the procedure, after baseline questionnaires and randomization, the participant will receive intraurethral lidocaine jelly as part of the standard pain control measures. Her bladder is then emptied using a Foley Catheter, and at the same time the bladder is then backfilled with 30 ml (300 mg/30 ml) of 1 % plain lidocaine solution. A waiting period of 30-50 minutes duration is allowed for the intravesicle lidocaine to take effect. During this wait period, participant is asked to lie supine for 10-15 minutes, then roll to the left side for 10-15 minutes and then to right side for about 10-15 minutes.

The participant, the provider taking care of the participant and the study coordinator assigned to the study will be blinded to the randomization. Both groups of participants will receive the TENS unit electrode placement during this wait period by the RN.

In participants randomized to the Active TENS group, the TENS unit will be initiated on standard setting (see ‘TENS, Electrode Placement, and Settings’) 5 minutes before starting the cystoscopy and will last the duration of the cystoscopy. The device intensity (amplitude) will be individually adjusted to each participant’s maximum sensory level, which is the strongest reported tingling feeling without pain and muscle contractions and kept at this setting for the duration of the procedure.

Participants randomized to the Sham TENS group will not receive the TENS therapy. Instead, they will receive electrode placement followed by initiation of the TENS unit until the participant feels the tingling sensation, following which the TENS unit will be immediately turned off by the RN. The participant will be notified by the RN that the TENS stimulus has been turned down such that they are not able to feel the tingling sensation anymore.

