7.2 Medical Monitoring

It is the responsibility of the Principal Investigator to oversee the safety of the study at his site. This safety monitoring will include careful assessment and appropriate reporting of adverse events as noted above, as well as the construction and implementation of a site data and safety-monitoring plan (see section 10 “Study Monitoring, Auditing, and Inspecting”). Medical monitoring will include a regular assessment of the number and type of serious adverse events.

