7.2.1 Internal Data and Safety Monitoring Board

An internal reviewer with Urogynecologic expertise will be appointed by the Obstetrics and Gynecology Research Chair who will participate in review of any serious adverse events associated with the trial. A meeting convened with the internal reviewer will be performed after 30 participants have undergone cystoscopic Onabotulinum Toxin A injection as part of the study.

8 Data Handling and Reporting

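### The only numerical safety halt covers the first 30 participants; no limit is stated for participants 31 to 60

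*Combined protocol and SAP*

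**What the plan says.** The second section numbered 7.1, Stopping Rules, plans one interim analysis once 30 participants have had the injection. If more than 3 serious adverse events (severe skin reactions, burns and muscle weakness are named) are "events reported in the 30 participants reviewed, further recruitment and administration of the TENS unit will be stopped". The study then goes on hold with the IRB while each event is examined for a causal link to the device. If none is shown, the investigators may ask the IRB to restart.

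Section 7.2.1 schedules the same single review: "A meeting convened with the internal reviewer will be performed after 30 participants have undergone cystoscopic Onabotulinum Toxin A injection". Section 4.3 plans 60 participants, 30 per arm, "expecting to enroll approximately 5 participants per month".

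Three provisions are not limited to the first 30:
- Section 7.3.1: for a serious event, the internal reviewer and "the Mayo Clinic IRB must be informed within 24 hours of the occurrence of the event". (The same section elsewhere limits IRB reports to directly related serious events.)
- Section 7.2, Medical Monitoring: "Medical monitoring will include a regular assessment of the number and type of serious adverse events".
- Section 7.2.1: an internal reviewer is appointed "who will participate in review of any serious adverse events associated with the trial".

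Medical Monitoring also calls for "the construction and implementation of a site data and safety-monitoring plan" and refers to section 10 under the title of the monitoring and auditing section. The section with that title is section 9, which covers access and audits and contains no safety limit.

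**The concern.** The sponsor has decided that 4 serious device-type events in 30 participants justify stopping recruitment and TENS use. Participants 31 to 60 have the same device, settings and procedure, yet the limit does not carry forward to them. As these documents stand, a cluster of the same size in the second half would lead to a hold only if someone judged that it should. That half is 30 of 60 participants, or 30 / 5 = 6 months of planned accrual. Medical Monitoring makes the Principal Investigator responsible for overseeing safety, and this is a setting in which a limit fixed in advance helps more than discretion.

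**Working it through.** The plan states no error rate or operating characteristic for its safety rule, so there is no figure to reproduce.

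**Inputs**
- Limit: more than 3, so 4 or more, in 30 participants of both arms together (Stopping Rules). 4/30 = 13.3%.
- Size: 60 participants, 1:1 (sections 4.3 and 5.2), so about 15 active participants in each half.
- Event rate: not given. Assumed 2%, 5% and 10% per participant at risk, with at most one event each.
- Who is at risk: two cases bracket this, because sham participants also have some exposure (section 5.2): "they will receive electrode placement followed by initiation of the TENS unit until the participant feels the tingling sensation". Case A: only the 15 active participants per half. Case B: all 30 per half.

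**Step 1. Chance that the limit is reached in one half**

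a = 1 − Σ(k=0..3) C(n,k) p^k (1−p)^(n−k)

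At p = 5%:
- Case A, n = 15: 1 − (0.46329 + 0.36576 + 0.13475 + 0.03073) = 0.00547.
- Case B, n = 30: 1 − (0.21464 + 0.33890 + 0.25864 + 0.12705) = 0.06077.

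**Step 2. First 30 pass, then 4 or more events in participants 31 to 60 with no stated halt**

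(1 − a) × a. At 5%: 0.99453 × 0.00547 = 0.0054 (A); 0.93923 × 0.06077 = 0.0571 (B).

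**Step 3. Chance of a hold if the limit applies to each block of 30**

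1 − (1 − a)². At 5%: 1 − 0.99453² = 0.0109 (A); 1 − 0.93923² = 0.1178 (B).

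**Step 4. Chance of a hold if the limit applies to any 30 consecutive participants**

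The 31 windows (1–30, 2–31, up to 31–60) overlap, so this was simulated with 800,000 sequences of 60 participants per setting. For Case A, balanced randomisation blocks of 2, 4, 6 and 10 gave the same results to the precision shown.

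| Rate | Case | Hold, present rule (a) | Uncovered cluster in 31–60 | Hold, each block of 30 | Hold, any 30 consecutive |
|---|---|---|---|---|---|
| 2% | A | 0.02% | 0.02% | 0.04% | 0.1% |
| 2% | B | 0.3% | 0.3% | 0.6% | 1.2% |
| 5% | A | 0.5% | 0.5% | 1.1% | 2.3% |
| 5% | B | 6.1% | 5.7% | 11.8% | 19% |
| 10% | A | 5.6% | 5.2% | 10.8% | 18% |
| 10% | B | 35% | 23% | 58% | 69% |

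**Step 5. What a separate limit per block would miss**

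The count restarts at participant 31. Three events in participants 25 to 30 and three in 31 to 36 would not stop the study. At a 5% rate, the chance that some run of 30 has more than 3 events while neither block does is the difference between the last two columns: about 1.2% (A) and 7.1% (B).

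**Sensitivity.** If a participant may have more than one event (Poisson, same mean), the each-block figures become 1.5% (A) and 12.7% (B) at 5%, and 12.7% and 58.1% at 10%. The picture does not change.

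**The case against.** The strongest reply is that the safeguard already exists in another form. Four serious events would be notified one by one, each within 24 hours, to an internal reviewer whose remit covers any such event. In a 60-participant study of a single procedure, with a method that the background section describes as safe, a second numerical trigger could be called a matter of taste.

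The benefit is also small on the figures above. The fourth event in a block tends to come late, with about 5 to 8 participants of that block still untreated on average. Multiplying by the chance of an uncovered cluster, a limit for participants 31 to 60 would spare at most about 0.03 (A) to 0.37 (B) participants per trial at a 5% rate. Even that supposes that nobody acts on four reports. The largest entries need both a 10% serious-event rate and equal risk on sham, although the sham unit is switched off once tingling is felt.

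Most of this stands, and it sets the weight of the point. It does not remove it: none of the continuing provisions states a count at which recruitment must stop, and nothing in the documents explains why the sponsor's own limit should lapse after participant 30.

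A reader might go further and infer that participants 31 to 60 have no safety monitoring. The documents contradict that: the reporting, the regular assessment and the reviewer's role all continue.

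**Conclusion.** The point holds as a minor gap that is cheap to close: these documents state no numerical halt for participants 31 to 60. At a 5% rate the uncovered-cluster probability is 0.5% to 5.7%, and at 2% it is negligible (0.02% to 0.3%). These sizes rest on assumed rates, independent participants and the two cases for who is at risk. The textual finding does not depend on them.

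Two limits apply. First, a separate site safety-monitoring plan may exist and may hold a limit; if so, a citation is all that is needed. Second, a reader might infer that a fourth event among the first 30 would be left until the meeting, so that about 5 to 8 more participants would be treated. That figure is conditional on reading the Stopping Rules to mean that the halt waits for the review. The section does not say so, and the 24-hour reports would already be with the internal reviewer. It should not be presented as a consequence of the plan.

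**What to change.** Reword the Stopping Rules to this effect: recruitment and TENS administration stop as soon as more than 3 serious adverse events of the kinds named in this Stopping Rules section (severe skin reactions, burns or muscle weakness) have been reported in any 30 consecutively treated participants, counted from the 24-hour serious-event reports. Keep the meeting at 30. If a site safety-monitoring plan already sets a limit for participants 31 to 60, cite it here instead.

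Name the counted events in the text and do not refer to them by section number. Two sections are numbered 7.1, and the list under Definitions includes skin irritation and muscle soreness, which would trigger holds far more often than costed here.

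The cost is a one-paragraph amendment and a higher chance of a temporary hold, which is reversible through the IRB route already described. From the present rule to the new one, that chance rises:
- at 2%: from 0.02% to 0.1% (A), from 0.3% to 1.2% (B);
- at 5%: from 0.5% to 2.3% (A), from 6.1% to 19% (B);
- at 10%: from 5.6% to 18% (A), from 35% to 69% (B).

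A simpler version, acceptable if the sponsor prefers it, applies the limit separately to participants 1 to 30 and 31 to 60 (1.1% and 11.8% at a 5% rate). It has the reset at participant 31 shown in the working.
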